The subclavian vein technique of access for the implant of CIED has been carried out for more than four decades without variations in it (23). It has the advantage of specifying a lower learning curve and being a fast and reliable way of access. The risk of pneumothorax, and the damage problems of the electrodes in the medium and long term, make this technique the least desirable as a way of first choice.

The technique of access through the axillary vein has been the subject of multiple improvements to become a technique that brings together advantages of the previous two (24-28). On the one hand, its speed and low incidence of complications and, on the other, its high effectiveness and capacity to accommodate a greater number of electrodes than the cephalic pathway. However, in our midst it is a technique of scant diffusion among the implanters.

There are some studies that compared the safety and efficacy of venous access techniques in the CIED implant.

Three studies have compared the axillary vein against the subclavian. The retrospective study of Sharma G et al (29), which included 478 patients undergoing a fluoroscopy-guided subclavian or axillary pacemaker implant, showed a similar efficacy of both techniques and a greater incidence of pneumothorax with the subclavian pathway. The retrospective study of Kim KH et al (30), which included 1161 patients with an average follow-up of 8 years, was able to objectively lower long-term incidence of electrode-related complications by the axillary pathway. Finally, the prospective and randomized study of Liu P et al (31) that compared the axillary pathway "optimized" against the subclavian pathway, found a 5 times greater incidence of peri-procedural complications with the second.

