Two studies have compared the axillary vein against cephalic. The prospective and randomized study of Calkins H et al (32) compared the safety and efficacy of CIED implant by cephalic access to axillary access guided by venography. It found a higher percentage of success and shorter duration of the procedure by the axillary pathway and there were no differences in the rate of peri-procedural complications. The limitation of this study is that the use of an axillary venous access technique guided by venography limits its applicability and increases the possible complications of the technique. The prospective and randomized study of Squara F et al (33) compared the safety and efficacy of CIED implant by Cephalic access to axillary access guided by fluoroscopy and performed by physicians without any training in the technique. This particular study found no difference in success or complications with both techniques, although it was objective a shorter time to get venous access by axillary. Finally, the prospective observational study of Chan NY et A (113) analyzed the success rate and long-term electrode problems of the techniques of cephalic, subclavian and axillary access guided by venography. The success of cephalic access was significantly lower than the other two. After an average follow-up of 73.6 months, the problem-free survival of the electrode was significantly higher with axillary and cephalic access.

3) Justification.

The studies published so far demonstrate the superiority of the axillary and cephalic venous accesses against subclavian venous access in the CIED implant in terms of efficacy and safety. However, the most widespread venous access technique in our midst remains the subclavian pathway.

There are no recommendations from scientific societies on which access road should be the first choice, so the technique used is totally dependent on the experience and preferences of the implant physician.

To date, there are no studies comparing axillary and cephalic venous accesses performed with the most optimized technique by trained personnel.

4) Hypothesis.

- The axillary venous access pathway is superior in terms of efficacy to the cephalic access.
- The axillary venous access pathway is equal in terms of safety to the cephalic access.

5) Main objective.

To compare the efficacy and safety of fluoroscopy-guided axillary venous access to improved cephalic venous access in the cardiac stimulation device implant.

6) Secondary Objectives:

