- To compare the success rate of the accesses.
- To compare the duration of access procedures.
- To compare the duration of the implant according to the access.
- To compare the proportion of peri-procedural complications of the accesses.
- To compare the proportion of electrode problems at follow-up.

7) Methodology.

Design: randomized and open clinical trial in parallel groups.

Study population: The reference population is the patients who are implanted for the first time a CIED. The target population of the study will consist of patients who were first implanted with a CIED at the General University Hospital of Ciudad Real.

Selection criteria.

-Inclusion criteria: adults patients (>18 years old) with CIED implant indication at the General University Hospital of Ciudad Real who agree to participate in the study.

-Exclusion criteria: patients with one or more of the following characteristics:

- * pre-existing ipsilateral electrode,
- * ipsilateral lymphadenectomy,
- * cardiac resynchronization therapy indication.

Sample size and sampling procedure.

It is estimated that a sample size of 240 patients is needed for the study to have a 80% statistical power, an alpha value of 0.05 and taking into account the estimated losses due to lack of monitoring and/or data.

The selection of cases that will form the sample shall be conducted by consecutive sampling of all patients who are going to implant a CIED, meet the inclusion and

exclusion criteria, and give their consent to participate in the study. The cases will be allocated to each group (axillary venous access or cephalic venous access) by a procedure of 1:1 randomization by balanced blocks. Sealed envelopes with the number assigned to each of the subjects to be included will contain a card in which the type of venous access assigned will be required.

Period and scope of recruitment.

Patient recruitment will begin in september 2017 and continue until the required sample size is reached with an estimated time limit in december 2019.

Every patient, once recruited and performed the implant of the CIED, will be followed in the same way: before the discharge hospital with review of the device, the surgical wound and the chest X-ray and, later, ambulatory controls at 3, 6, 12 and 24 months of the Device and the generator bag.

The follow-up time will end with the completion of the study, but it may be sooner if the patient dies or moves from the hospital.

Variables:

1. Independent:

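### The single 80% power figure is stated for a study that includes an equal-safety hypothesis, but no safety rate or margin supports it, and a non-significant safety test at this size would not show equality

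*Combined protocol and SAP*

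**What the plan says.** Section 7 (Sample size and sampling procedure) gives one sentence on power: "It is estimated that a sample size of 240 patients is needed for the study to have a 80% statistical power", with "an alpha value of 0.05" and "taking into account the estimated losses due to lack of monitoring and/or data". Allocation is "by a procedure of 1:1 randomization by balanced blocks", so 240 means 120 per arm. The sentence names no endpoint, rate, standard deviation, target effect, margin, sidedness or loss rate.

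Section 5 states one main objective: "To compare the efficacy and safety of fluoroscopy-guided axillary venous access to improved cephalic venous access". Section 4 has two hypotheses. The first is "The axillary venous access pathway is superior in terms of efficacy to the cephalic access"; the second is that the accesses are equal in safety.

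On safety rates, section 2 (Introduction) says that cephalic access has had no pneumothorax in the short term, and it credits the axillary technique with "its speed and low incidence of complications". It gives no complication rate for axillary access and no overall rate for either arm. Section 7 lists several safety outcomes under Variables and selects none as primary. Section 9 compares categorical outcomes with a chi-square test at p < 0.05. It mentions no confidence interval, equivalence test or non-inferiority test.

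**The concern.** The 80% is attributed to the study as a whole, and safety is half of the main objective and one of only two hypotheses. A reader may fairly take the figure to cover safety. The only analysis planned for the equal-safety hypothesis is a test of difference, so a non-significant p-value is the only result in the plan that could be offered in its support.

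If power for safety is in fact low, a real excess of complications in one arm would usually give p > 0.05 and could be reported as equal safety from a trial with 80% power. That matters because section 10 justifies the trial by the absence of recommendations on which access to choose first.

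**Working it through.** **1. The plan's own figure.** The 240 cannot be reproduced, because the endpoint, effect, variability, margin, sidedness and loss rate are all missing. The check therefore takes 120 per arm as given and asks what it delivers for safety.

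**2. Inputs.**
- From the documents: 240 patients, 1:1, alpha 0.05, chi-square test, and 0% cephalic pneumothorax.
- Assumed: a two-sided test, all other event rates, and all margins. For losses, 10% is assumed, leaving 120 × 0.9 = 108 per arm.

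**3. Power to detect a difference.** Power is the sum of the binomial probabilities of all outcome pairs (a, b) for which the uncorrected chi-square exceeds 3.84. With n per arm, chi-square = 2n(a − b)² / [(a + b)(2n − a − b)].

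The pneumothorax case can be followed by hand. With 0 events in one arm and k in the other, chi-square = 240k / (240 − k). This is 3.04 for k = 3 and 4.07 for k = 4, so at least 4 events against 0 are needed. With 120 patients at a true 2%, P(4 or more) = 0.220.

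| Assumed rates | Power, 120 per arm | Power, 108 per arm |
|---|---|---|
| 0% vs 2% | 22% | 17% |
| 2% vs 4% | 13% | 12% |
| 5% vs 10% | 32.5% | 29% |
| 10% vs 20% | 59% | 55% |
| 0% vs 4.6% | 81% | 74% |
| 5% vs 15.6% | 80% | 76% |

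Without losses, 80% is reached at an excess of about 4.6 points from 0% and 15.6 − 5 = 10.6 points from 5%. By the usual normal-approximation formula, detecting a doubling with 80% power needs about 435 per arm from 5% and 1141 per arm from 2%.

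**4. Power to support equality through a margin.** Assume the same true rate p in both arms and a non-inferiority test at one-sided 0.025. The smallest margin with 80% power is (1.960 + 0.842) × √[2p(1 − p)/120]:
- p = 1%: 2.802 × 0.01285 = 3.6 points
- p = 2%: 2.802 × 0.01807 = 5.1 points
- p = 5%: 2.802 × 0.02814 = 7.9 points

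Each margin exceeds the event rate itself: 3.6 times at 1%, about 2.5 times at 2% and 1.6 times at 5%. For a fixed 5-point margin, power is 97% at a 1% rate, 79% at 2%, 62% at 3% and 43% at 5%. For a 10-point margin at 5% it is 94%. These are normal approximations and are rough at 1%, where only 120 × 0.01 = 1.2 events per arm are expected.

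**5. What an interval would show.** With 0 events in 120, the upper limit of the exact 95% interval is 1 − 0.025^(1/120) = 3.0%. Even an arm with no events would leave a rate of up to 3% open.

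**6. Could the 80% belong to efficacy?** Section 2 puts cephalic effectiveness below 85% and gives no axillary rate. Taking 85% against an assumed 95%, exact power at 120 per arm is 76%. At 80% against an assumed 93%, it is 86%. The answer depends on rates that the plan does not state.

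**The case against.** The strongest reply is that the rates and margins above are assumptions. The documents give one safety rate, 0% pneumothorax with cephalic access, and a qualitative remark about axillary access. A reader might go further and infer that 240 patients cannot give 80% power for safety at all. The documents do not support that. Power reaches 81% for 0% vs 4.6%, 97% for a 5-point margin at a 1% rate and 94% for a 10-point margin at 5%. For a fixed absolute margin, rarer events raise power, so rarity alone does not defeat the equality aim. Whether 80% is attainable depends on a margin or target difference that the plan never sets. This part of the objection stands, and the point is limited accordingly.

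A reader might also infer that the 80% should simply be assigned to efficacy. That does not follow either. The efficacy power is just as unverifiable, and it falls on either side of 80% under equally plausible assumed rates.

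Finally, it can be said that this is only the missing-endpoint problem again. That is partly so. But naming an efficacy endpoint for the 240 would still leave the equal-safety hypothesis with no margin, no matching analysis and low power to detect a doubling of complications.

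**Conclusion.** The concern holds in limited form. The plan states one 80% power for a study whose main objective and second hypothesis include safety, and nothing in it supports that figure for safety. Under the assumed rates, exact power with 120 per arm is 13% to 59% for a doubling from 2%, 5% or 10%, and 22% for 0% vs 2%. The range for the same doublings is 12% to 55%, and the pneumothorax figure 17%, at an assumed 108 per arm. Attaining 80% needs a large excess or a margin wider than the event rate, and the plan states neither as its target. A non-significant chi-square test could not be read as equal safety.

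The documents do not show that 80% is impossible for every safety outcome and margin, nor that the 80% was calculated for efficacy. The result rests on the assumed rates, a two-sided 5% test and, for the margins, equal true rates in both arms.

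**What to change.** In section 7, state that the 80% power is not claimed for the safety comparison. Name the endpoint for which 240 was calculated, with its rates or standard deviation, target effect, sidedness and loss rate. Do not assign the 80% to efficacy unless that calculation supports it.

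In section 9, report each safety outcome as a risk difference with a 95% confidence interval, using an exact or score-based method for rare events. State that no conclusion of equal safety will be drawn from p > 0.05.

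The cost is protocol wording, minor analysis work and a less favourable power statement. No extra patients are needed.

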Cardiac implantable electronic devices (CIED) are essential therapeutic tools for the management of arrhythmias in different clinical contexts (1, 2). Under the name of CIED are grouped pacemakers and cardiac defibrillators. Worldwide, more than 1 million implants of these devices are carried out annually (3). In Spain CIED implants are made in 230 centers, 4 most CIED are implanted in electrophysiology laboratories by electrophysiologist and the number of implants follows an increasing trend, being in the year 2015 the incidence of pacemaker first implantations/million inhabitants of 611 and that of defibrillators of 118 (5, 6).

A fundamental step in the implant procedure of a CIED is to establish a central venous access in order to insert the electrode catheters and place them in the cardiac chambers. In most procedures ($> 80\%$) it is accessed by the left axilo-subclavian axis, reserving the right side for left-handed patients or with vascular problems on the lefthand side. According to data from the European Heart Rhytm Association (7), 60% of implanters use as a preferential access vein cephalic, 20% axillary vein and 20% subclavian. In our midst, however, this proportion is quite different, with subclavian access being much more widespread.

The access route for the implant of a CIED has prognostic implications. Cephalic access has shown, in the short term, a null incidence of pneumothorax compared with the axillary or subclavian pathway, (8-10) because it does not require puncturing the subclavian region. On the other hand, in the medium and long term, when the access roads are compared, the subclavian approach has been related to a higher incidence of electrode problems as insulation defects and conductor fractures (11-13) which seems due to anatomical factors that condition the electrode's crush (14).

The technique of access through the cephalic vein for the implant of CIED has been carried out for more than five decades (15). Since it requires greater surgical dexterity, it was initially performed preferably by thoracic or cardiac surgeons. With the time, thanks to the technical improvements that have increased their percentage of effectiveness (16-22). However, the main problem for its universalization remains the

lack of knowledge of the technique on the part of many operators and an effectiveness of less than 85%.

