Age, sex, hypertension, diabetes, dyslipidemia, obesity, type of heart disease, renal failure, COPD, CIED indication, type of implanted CIED, assigned access route, number of implanted electrodes, type of electrode implanted.

2. Dependents:

- Efficacy: success of assigned access, duration of the access technique, duration of the procedure, time of copying, cephalic canalization, axillary canalization, finally canalized route, main cause in case of failure.
- Safety: Complications of the procedure, Pneumothorax, hematoma, dislocation electrode, venous thrombosis, long-term electrode problems, insulation defect, driver's fracture, need for new electrode implant.

8) Phases of the project and Plan of work.

The research project will be carried out in the arrhythmia unit of the General University Hospital of Ciudad Real. The two investigators will be in charge of the recruitment of the patients, the implant of the CIED and the data collection. The principal investigator will be in charge of the analysis of the data. Advice and collaboration for analysis will be requested from the HGUCR Research support unit. The commencement of recruitment will be in the fourth quarter of 2017 and completion in the fourth quarter of 2019. No funding is necessary for the realization of the project.

9) Sources of information and data analysis.

The data for the study will be obtained from the patient himself (data of filiation and personal history), of the data collection sheet that will be filled during the implant and in the postoperative and the ambulatory monitoring of the device. All data will be entered in a database with SPSS software for further analysis.

The quantitative variables will be represented by means of the mean +/-standard deviation and the qualitative variables as percentages.

To evaluate the degree of adjustment to the normality of the quantitative variables will be used the test Kolmogorov-Smirnov.

The comparison between the two study groups will be done through an intention-to-treat analysis. The comparison of quantitative and qualitative variables will be carried out with the Student's t test. The comparison of quantitative and qualitative variables with the test of the U of Mann-Withney and the comparison of two Qualitative variables with the χ^2 test. A logistics linear regression analysis will be used for multivariate analysis.

A level of statistical significance shall be considered a value of $p < 0.05$.

10) Ethical aspects.

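### The only lead count listed is the number implanted, known after the access attempt; the planned number should be fixed before allocation and used as the covariate instead

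*Combined protocol and SAP*

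**What the plan says.** Eligibility (section 7, Selection criteria) is any adult with an indication for a device. The only device-based exclusion is "cardiac resynchronization therapy indication". Section 1 describes implants with one or more electrodes, and section 2 says that the axillary route has "capacity to accommodate a greater number of electrodes than the cephalic pathway".

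Allocation (section 7, Sample size and sampling procedure) is by a "procedure of 1:1 randomization by balanced blocks", using sealed envelopes whose card states the assigned access. No stratification factor is named, and no step records the intended system before the envelope is opened. The trial is open. Section 8 has the same two investigators recruit, implant and collect the data.

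The independent variables in section 7 include the device indication, the type of device implanted, the assigned route and the "number of implanted electrodes". A planned number of leads is not listed. Section 9 specifies an intention-to-treat comparison with simple two-group tests, and a multivariate regression for which no covariates are named.

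**The concern.** The protocol itself names lead capacity as a difference between the two veins, so lead number is a plausible influence on access success and on access and implant duration. A useful covariate of this kind has to be settled before allocation. The count on the list is settled afterwards, by operators who know the arm and are working through the assigned vein.

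The implanted number sits beside age, sex and the assigned route as an independent variable, so it is a natural candidate for a regression with no covariate list. If the assigned vein affects how many leads are placed, patients with the same implanted number in the two arms are no longer comparable, and the adjusted access effect loses the protection of randomisation. Intention-to-treat does not prevent this, because it fixes the arm and not the covariate. The plan also gives up the modest precision that a proper baseline covariate would bring.

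**Working it through.** **1. The plan's own figure.** The documents state that "a sample size of 240 patients is needed for the study to have a 80% statistical power", with "an alpha value of 0.05". They do not give the endpoint, effect size, sidedness or loss rate, so 240 can be neither confirmed nor refuted. Assumed success rates of 80% against 93% (two-sided) need 216, and 216/0.90 = 240 with 10% loss. Rates of 85% against 95% (two-sided) need 282. The point here does not depend on which was meant. I take 240 as given, 120 per arm.

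**2. Assumed inputs (none is in the documents).** Two-lead share 60% (30% to 70% as a check); within-group SD of implant time 20 minutes; two-lead implants 10 or 20 minutes longer. One and two leads is my reading of one or more electrodes with resynchronisation excluded.

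**3. Chance imbalance without stratification.**
- SE of the between-arm difference in two-lead share = sqrt(2 × 0.6 × 0.4 / 120) = 0.063.
- 95% range = ±1.96 × 0.063 = ±12.4 points.
- For shares of 30% to 70% the range is ±11.6 to ±12.7 points. Simulated unstratified blocks (size 4 assumed) agree, with about an 8% to 12% chance of a difference above 10 points.
- At the 95% limit, mean implant time shifts by 0.124 × 20 = 2.5 minutes, or 0.124 × 10 = 1.2 minutes.

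**4. Comparison with ordinary sampling error (20-minute case).**
- Variance due to lead number = 0.6 × 0.4 × 20² = 96; total = 96 + 400 = 496.
- Unadjusted SE of the mean difference = sqrt(2 × 496 / 120) = 2.88 minutes.
- The 2.5-minute shift is below one SE and is already contained in it.

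**5. Precision gained by adjusting for planned number.**

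| Extra time with two leads | Share of variance | Equivalent N |
|---|---|---|
| 20 min | 96/496 = 0.194 | 240/(1 − 0.194) = 298 |
| 10 min | 24/424 = 0.057 | 240/(1 − 0.057) = 254 |

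In the 20-minute case the SE falls to sqrt(2 × 400 / 120) = 2.58 minutes, and the 95% half-width from 1.96 × 2.88 = 5.6 to 1.96 × 2.58 = 5.1 minutes. These equivalents apply to implant time only. They do not carry over to a logistic model for access success.

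**6. Access success.** If success differs by 5 to 20 points between one- and two-lead implants (assumed), a 95%-limit imbalance shifts the crude difference by about 0.6 (0.116 × 5) to 2.5 (0.127 × 20) points. At assumed rates of 85% and 95%, the SE of that difference is sqrt(0.85 × 0.15/120 + 0.95 × 0.05/120) = 0.038, or 3.8 points. Again the shift is below one SE.

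**7. Conditioning on the implanted number.** At 60% two-lead, each arm expects 72 planned two-lead and 48 planned one-lead patients. Purely to show the mechanism, suppose 5% of the 72 in the cephalic arm ended with one lead: 0.05 × 72 = 3.6. The implanted-one-lead group would then be 48 + 3.6 = 51.6 in that arm against 48 in the other, and 3.6/51.6 = 7% of it would be patients with no counterpart in the axillary group. If no such departures occur, the planned and implanted counts agree and there is no harm. The variables listed do not show which case holds.

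**The case against.** The strongest objection is that unstratified randomisation is valid. Lead-number imbalance is random, the usual standard error already covers it, and steps 4 and 6 confirm that it is small. This stands: a reader might infer that the lack of strata biases the comparison, and it does not. The gain in step 5 also comes from adjustment, not from separate envelope series, so it gives no reason to restratify during recruitment.

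Second, the documents describe no reduction from two leads to one. A reader might infer that such patients would be scored as quick cephalic successes, but nothing in the text says so. The data sheet collects canalisation by each vein, the route finally used and the main cause of failure, which could reveal a partial result. One cited title even concerns placing two leads through the cephalic vein. This also stands. What remains is that the implanted number is open to influence by the arm, not that it will be influenced.

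Third, it would be too strong to say that the intended system goes unrecorded. The indication is collected separately from the implanted device type, and the planned number may be recoverable from it. The documents do not say that it states lead number.

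Fourth, the regression names no covariates, so adjustment for the implanted number is not actually planned. True, but its place among the independent variables leaves it available, and nothing rules it out.

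Finally, a reader might want success redefined as all planned leads passing through the assigned vein. Changing an efficacy definition partway through an open trial invites suspicion of a data-driven choice, and this point does not need it.

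**Conclusion.** The concern holds in a limited form. The trial mixes implants with different lead numbers, the protocol says that the veins differ in lead capacity, and the only listed count arises after allocation while being classed as independent. Replacing it with the planned number removes the risk of post-randomisation adjustment and adds modest precision: about 254 to 298 equivalent patients for implant time, on inputs that are all assumed. Neither bias from unstratified allocation nor actual changes of plan by arm can be claimed from the documents. Severity is optional to minor.

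**What to change.** - Record the planned number of leads on the data sheet before the envelope is opened. The document is dated October 2018 and recruitment was to start in 2017, so for patients already enrolled take the number from the pre-procedure indication, abstracted without reference to arm or outcome.
- In section 9, name planned lead number as a pre-specified covariate in the comparisons of access success (logistic model) and of access and implant duration (linear model). State that the implanted number will not be used for adjustment.
- Report access success by planned lead number.
- Keep the implanted number as a descriptive outcome by arm, so that any departure from plan is visible.
- Stratified envelopes for the remaining recruitment are optional.

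The cost is one form field, a retrospective abstraction for enrolled patients and one model term. The sample size does not change, and the fix implies nothing about which device or how many leads a patient should receive.

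### The electrode-problem proportion is not tied to the 24-month control and ignores time at risk, so the reported risk can fall slightly below the true 24-month risk

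*Combined protocol and SAP*

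**What the plan says.** Four parts of the protocol bear on this.

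- **Section 7, Period and scope of recruitment.** The follow-up scheme is common to all: "Every patient, once recruited and performed the implant of the CIED, will be followed in the same way". After the pre-discharge check come "ambulatory controls at 3, 6, 12 and 24 months". The next sentence governs when follow-up stops: "The follow-up time will end with the completion of the study, but it may be sooner if the patient dies or moves". No date or event defines study completion. On accrual the section says: "Patient recruitment will begin in september 2017 and continue until the required sample size is reached with an estimated time limit in december 2019".
- **Section 6, Secondary Objectives.** The fifth objective reads "To compare the proportion of electrode problems at follow-up". No month is given. The safety variables in section 7 include "venous thrombosis, long-term electrode problems, insulation defect", followed by conductor fracture and the need for a new electrode. These have no time point either.
- **Section 8.** "The commencement of recruitment will be in the fourth quarter of 2017 and completion in the fourth quarter of 2019". The sentence opens with recruitment and agrees with the December 2019 recruitment limit in section 7, so it most likely dates the end of recruitment and not the end of the study.
- **Section 9.** Groups are compared by intention to treat. For a binary outcome the plan gives "the comparison of two Qualitative variables with the χ^2 test", with logistic regression as the multivariate method. There is no time-to-event method and no rule for counting patients who die, move or are cut off.

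**The concern.** An electrode problem is an outcome that accumulates over time, so a percentage means something only with a horizon attached. Here the visit schedule points to 24 months, but the stopping sentence does not, and the analysis does not use each patient's length of observation. A patient who transfers at month 5 without a problem then enters the crude proportion exactly like one who was checked at month 24 without a problem.

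At stake is how well the reported percentage estimates the 24-month risk in each arm. This is also the one secondary objective that looks at the longer term. The introduction motivates it with lead damage in the medium and long term and cites studies with mean follow-up of 8 years and 73.6 months. A percentage without a stated horizon is hard to set beside such results.

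**Working it through.** **Inputs from the documents:** 240 patients allocated 1:1, so 120 per arm; recruitment from September 2017 to December 2019; last listed control at 24 months. The protocol gives no electrode-problem rate, loss rate or study-end date, so there is no figure of its own to reproduce here.

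**Assumptions:** a 24-month risk *r* of 5% (2% and 10% also tried); Weibull risk F(t) = 1 − (1 − r)^((t/24)^k), with k = 0.5, 1 or 2 for falling, constant or rising hazard; transfer at a constant rate, with a share *L* lost by 24 months; uniform accrual. Month 0 is 1 September 2017 and month 28 is the end of December 2019.

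**1. Who can reach 24 months.** If the study closes at the last patient's 24-month control (month 28 + 24 = 52, December 2021), everyone can. Only transfer then shortens observation.

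**2. Crude proportion with transfer, counting to 24 months.** With transferred patients kept in the denominator, the expected crude proportion is the integral from 0 to 24 of f(t)·(1 − L)^(t/24) dt, where f is the density of F. For constant hazard this has a closed form. Put a = −ln(1 − r) and b = −ln(1 − L); then

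observed = a/(a + b) × [1 − (1 − r)(1 − L)].

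For r = 5%, L = 20%: a = 0.0513, b = 0.2231, so 0.0513/0.2744 × (1 − 0.95 × 0.80) = 0.1869 × 0.24 = 4.49%.

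Observed as a fraction of the true 5%:

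| Transfer by 24 months | Falling hazard | Constant | Rising |
|---|---|---|---|
| 5% | 0.983 | 0.975 | 0.967 |
| 10% | 0.966 | 0.950 | 0.933 |
| 15% | 0.949 | 0.924 | 0.898 |
| 20% | 0.931 | 0.897 | 0.864 |

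The extremes are 0.983 × 5% = 4.9% and 0.864 × 5% = 4.3%. The ratios change by no more than 0.001 at a 2% or 10% risk.

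**3. Unequal transfer between arms.** With equal 5% risk, constant hazard and transfer of 5% v 15%, the crude proportions are 4.88% v 4.62%, a spurious difference of about 0.3 points.

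**4. Sampling error for comparison.** The 95% CI half-width for a difference is 1.96 × √(2r(1 − r)/120). At r = 5% this is 1.96 × √(0.095/120) = 5.5 points; at 2% it is 3.5 (a rough approximation with so few events) and at 10% it is 7.6. Expected events in 240 patients are 4.8, 12 and 24 at 2%, 5% and 10%.

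**5. Death.** If patients who die stay in the denominator and there is no transfer or cut-off, the crude 24-month proportion already equals the cumulative incidence with death as a competing event. Death alone needs no correction.

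**6. Sensitivity to an early close.** If the study closed in December 2019 (month 28), the share able to reach 24 months would be (28 − 24)/28 = 14% with a September 2017 start, or none if accrual began in January 2018, the latest start tried. With the September start the crude proportion would be 0.718, 0.575 or 0.432 of the 24-month risk for falling, constant or rising hazard. With a close in December 2020 (month 40), (40 − 24)/28 = 57% could reach 24 months, and the ratios are 0.942, 0.895 and 0.824.

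**The case against.** The strongest reply is that the horizon is there in all but name. All patients follow one scheme, 24 months is its last control, and the natural reading of the objective is the proportion found over that scheme. The stopping sentence can even be read to mean that a patient finishes when the schedule is complete. Much of this stands: 24 months is implied. It is not stated, however, and the wording equally allows a common closing date that cuts off late recruits. Nor does this reading settle how transferred patients are counted.

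A second reply is that randomization protects the comparison. This also stands for administrative cut-off: with balanced blocks over one accrual period, closing dates fall alike on both arms and the chi-square test remains valid. Only transfer that differs by arm could bias the comparison, and step 3 shows that effect to be small beside the sampling error.

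A third is that intention to treat already keeps deaths in the denominator. That is fair, and step 5 agrees. Transfer and cut-off remain.

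Two stronger readings are tempting, and the documents support neither. A reader might take the fourth-quarter 2019 date in section 8 as the study's end and infer that almost nobody reaches 24 months; the sentence concerns recruitment. A reader might also infer inflation well above the 24-month risk, from problems counted up to a common closing date. Under the assumptions above, with a December 2021 close, 5% would become 6.2%, 7.8% or 12.4% for falling, constant or rising hazard. But no control is listed after 24 months, so this is an upper bound and not the plan's likely behaviour.

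**Conclusion.** The concern holds as a minor point about estimation. The plan implies a 24-month horizon but does not fix it, and a crude proportion takes no account of shorter observation. On the likelier reading, with counting to 24 months and 5–20% transfer, an assumed 5% risk would be reported as about 4.9–4.3%. Risk, transfer rate, hazard shape and accrual pattern are all assumptions. The gap in the wording does not depend on them.

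A reader might infer that the between-arm test is invalid or that the trial's conclusions are at risk. The documents do not support that: the test stands for administrative cut-off, likely bias from unequal transfer is well inside the sampling error, and four of the five secondary objectives (access success, access duration, implant duration and peri-procedural complications) are untouched. A materially larger understatement would need an early study close, which is not the likelier reading.

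**What to change.** - **Section 6:** set the electrode objective at the existing 24-month control.
- **Section 7:** define study completion so that it agrees with that control, for example as the last patient's 24-month control.
- **Section 9:** replace the crude proportion with the cumulative incidence of a first electrode problem per patient at 24 months, by arm, with a 95% CI for the difference. Censor at transfer or data cut-off and treat death as a competing event. State that problems found at the 24-month control count, with a visit window, because scheduled controls date a problem only to an interval. Report by arm the numbers followed to each control.

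A log-rank or Cox comparison is optional, given the roughly 5–24 events expected under the assumed risks.

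The cost is a few clauses and a small extra analysis on implant, visit, event, death and transfer dates from the planned follow-up. No visits are added. If completion is set at the last patient's 24-month control, the electrode report comes later. Were the study closed early instead, the analysis would handle the shorter follow-up but would not recover the events missed.
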